9.5 Study Endpoints

The primary outcome is the BF continuation rate at 6-month postpartum. This is determined by observed breastfeeding which includes: audible swallowing, regular suck/swallow/breath patters, visible milk in the infant's mouth after the infant is not latched anymore. Or, in the case of pumping moms, pumped milk and successful feeding to the infant. We hypothesize that the isolated effect of monthly incentives contingent on BF in SC+BFI will increase BF rates by 25% at 6-month compared to SC.

The exploratory outcome is the BF continuation rate at 12-month postpartum. We will hypothesize that SC+BFI will increase the BF rate at 12-month, compared to SC.

10.0 Study Procedures Involved:

- 10.1 We will use a randomized, two-group design (Standard Care+Breastfeeding Support vs. Standard Care+Breastfeeding Incentives).
- 10.2 We will use a permuted block random assignment (with block size = 6), assigning participants to one of 2 groups: *Standard Care* or *Standard Care + BFI*. This will allow us to keep group sizes approximately equivalent during the study maintaining an approximately equal size for the 2 groups. We will use propensity score matching to randomize the participants based on study site, as well as Black race and Puerto Rican ethnicity to maximize internal validity.

Allocation to study groups in randomization will be administered by [name] (Co-I) who will not have access to collected data until the end of the study. [name] will generate computer-

generated random numbers and keeps the original sequence in a password-protected electronic file that no other research staff can access. [name] will program the list of random numbers into an electronic file on RedCap which will automatically assign each participant to either condition. Other research staff can only view the result of randomization so that the allocation process remains concealed.

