Home-based support and problem-solving component: Blinded RA will also provide individual support and problem-solving in addition to WIC services. At each monthly home visit, blinded RA will ask participants to demonstrate BF, praise participants' efforts to continue BF, problem-solve issues around BF, provide local BF resources, and identify any issues with BF and other medical and psychosocial needs. Signs to verify ongoing BF include audible swallowing of breastmilk, regular suck/swallow/breathing patterns, visible milk in an infant's mouth, and (in case of pumping moms) pumped milk and successful feeding of an infant. When a participant has trouble with BF, she will be referred to a certified lactation consultant (CLC). Should a participant report any adverse maternal and infant outcome during the study period, blinded RA will document the event, report to the PI and IRBs, and make referrals as needed. Participants in SC will be asked to monitor their nutritional habit each month and to complete 24-hour recalls for each month. Research staff will mark a tally on a checklist at each monthly visit, and completion of nutritional monitoring will lead to a lump sum compensation for a total potential earning of \$240 with \$40 per completed monthly nutritional monitoring. Participants will also receive diapers and wipes at every home visit. This is comparable to the SC+BFI group to control for the incentive amount. However, in SC, this payment is tied to monitoring the nutritional habit and paid in a lump sum— not to observed BF at each month as in the SC+BFI group.

If a participant misses an appointment, this will be counted as incompliance with monthly nutritional monitoring. The participant will be given an opportunity to make up for the missed appointment within one-week timeframe from a due date. Blinded RA will contact a participant a week prior to the due date and make an appointment. After 3 attempts to reach a participant by

phone, blinded RA will provide a daytime unannounced home visit. Participants will be informed of potential unannounced home visits during study consent.

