Standard Care + Breastfeeding Incentives (SC+BFI). Participants in *SC+BFI* will receive all WIC usual care elements the *SC* group receives, plus (the only element that is different between groups) an escalating amount of monthly financial incentives contingent on observed BF and that incentives will be delivered immediately upon verified BF at each month. This will isolate the component of contingent incentives on BF which is hypothesized to produce the largest effect on continued BF rates. Blinded RA will ask participants to demonstrate BF and provide individual support to praise efforts to continue BF and problem-solve BF issues.

Contingent incentive component: The incentive amount was \$20.00 at the end of the first month and increased by \$10.00 every month until the end of 6 months. The maximum potential earning is \$270.00. The initial incentive value of \$20 was determined in the pilot study based on inputs from WIC-receiving Puerto Rican mothers as the minimum amount of monthly incentives that would motivate them to breastfeed (not to substitute for compensation from work outside of home). An escalating schedule of monthly incentives was employed based on previous incentive-based interventions to encourage continuous abstinence from substance use. A participant who successfully demonstrates BF receives the incentive amount on a pre-paid credit card at the end of each month. If a participant misses an appointment or does not demonstrate BF, she will not receive the incentive. The rest of the procedure will be the same as for *SC*. We will also provide bonus incentives of \$50 to mothers who selected full BF food package from WIC at baseline, 3 months and 6 months postpartum. Selection of the WIC food package will be verified through WIC.

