12.0 Withdrawal of Subjects

- 12.1** If women are incarcerated during 6 months of study participation, and if participants fail to attend scheduled visits during 6 months of study participation for more than 3 months, participants may

be subject to study withdrawal without their consent. Participants deemed eligible for study withdrawal by the PI will be informed of the decision by phone or mail.

Participants who were terminated on their study participation will not be followed up for periodic assessments or monthly home visitations. However, if participants need assistance in breastfeeding and other psychosocial issues, research staff provides referrals to appropriate community and hospital services.

13.0 Potential Benefits to Participants:

- 13.1** We believe that the aforementioned risks are reasonable in relation to the anticipated benefits to the mother and infant from continued BF. Participants receive direct benefits from participating in the study to increase access to existing breastfeeding support available in the community. Participants in the SC+BFI group may also experience increased motivation and confidence to continue breastfeeding for 6 months and beyond. In addition, the proposed project has the potential to provide important new scientific information regarding developing effective strategies for maintaining BF during 12 months. We believe the combined direct therapeutic benefits to subjects and new scientific information to be gained in the proposed studies outweigh any risks involved.

14.0 Financial Compensation:

- 14.1** There are three kinds of financial compensations involved in the study.
- 1) Contingent incentives on breastfeeding for participants in SC+BFI: This will be paid immediately and remotely on a Master Card as soon as breastfeeding is confirmed. The amount in the first month home visitation will be \$20, increasing by \$10 every month, for a total potential earning of \$270. Participants in this group will also be eligible to receive \$50 per selection of full breastfeeding food package at WIC at baseline, 3 months, and 6 months postpartum. Thus, a potential total earning in this group is \$420.
 - 2) Incentives on home visitations for participants in SC: This will be paid at the end of 6 months based on the number of completed home visitations. The amount per home visit will be \$40 for a total potential earning of \$240. This will be paid in form of retail gift cards.

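### The protocol says the monthly breastfeeding incentive is the only difference between arms, but SC+BFI alone can also earn a WIC food-package bonus, so the trial can conclude only on the payment package

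*Combined protocol and SAP*

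**What the plan says.** Three statements claim that the design isolates one component.

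- Section 10.3 (SC+BFI) says these mothers receive what SC receives, "plus (the only element that is different between groups) an escalating amount of monthly financial incentives contingent on observed BF", paid at once when BF is verified. It adds: "This will isolate the component of contingent incentives on BF which is hypothesized to produce the largest effect on continued BF rates".
- Section 10.3 (home-based support component) says of the SC payment: "This is comparable to the SC+BFI group to control for the incentive amount".
- Section 9.5, and 4.2 in the same terms, state the primary hypothesis: "We hypothesize that the isolated effect of monthly incentives contingent on BF in SC+BFI will increase BF rates by 25% at 6-month".

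The payment provisions say more.

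- Section 10.3 (contingent incentive component) adds a $50 bonus for "mothers who selected full BF food package from WIC at baseline, 3 months and 6 months postpartum", verified through WIC. Section 10.2 lists this bonus among the differences between arms.
- Section 14.1 gives the SC+BFI ceiling, bonus included: "Thus, a potential total earning in this group is" $420. It gives SC a ceiling of $240.
- Section 10.5 pays the SC+BFI incentive on a pre-paid card and the SC lump sum in retail gift cards.

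**The concern.** The bonus is a second incentive, offered in one arm only. It is not monthly, and it rewards a choice made at WIC rather than BF seen at a home visit. The bonus and the form of payment both lie outside the one element that 10.3 says differs.

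If SC+BFI does better at 6 months, the result could reflect the incentive for observed BF, the food-package bonus, the larger amount on offer, the form of payment, or some mix. No third arm separates these, and the SAP plans no analysis that does. The primary hypothesis as worded would then be declared confirmed by data that cannot distinguish it from the alternatives. This matters beyond the wording: the stakeholder interviews (Aim 4) and the cost-effectiveness work (Aim 5) need to know which payments the effect came with.

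**Working it through.** **Inputs.** SC+BFI monthly schedule: $20 rising by $10 to $70 over six visits (10.2, 10.3). Bonus: $50 at up to three time points, SC+BFI only (10.2, 10.3, 14.1). SC: $40 for each of six months (10.3, 14.1). Assessment pay in both arms: $20 at 1, 3 and 6 months and $40 at baseline, 9 and 12 months (14.1). Pilot mean earned from monthly incentives: $199, SD $106 (5.3).

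**The plan's own ceilings reproduce.**
- Monthly incentives: 20 + 30 + 40 + 50 + 60 + 70 = $270.
- Bonus: 3 x 50 = $150.
- SC+BFI total: 270 + 150 = $420.
- SC total: 6 x 40 = $240.

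**Is the amount controlled at the ceiling?**
- Monthly payments alone: 270 - 240 = $30, and 30/240 = 12.5%. This is roughly comparable.
- With the bonus: 420 - 240 = $180, and 420/240 = 1.75.
- Bonus share of the gap: 150/180 = 83%. Bonus share of the SC+BFI ceiling: 150/420 = 36%.
- Assessment pay adds 3 x 20 + 3 x 40 = $180 to each arm, giving $600 vs $420. The $180 gap is unchanged.
- Through month 3, the SC+BFI ceiling is 20 + 30 + 40 = $90 for observed BF and 2 x 50 = $100 in bonuses. The bonus is therefore 100/190 = 53% of what can be earned by then.

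**What might actually be paid?** Bonus uptake is not given. Assume that the pilot mean of $199 carries over, that mothers earn 0 to 3 bonuses on average, and that every SC mother completes all six months ($240).

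| Bonuses earned | Mean SC+BFI pay | Difference from $240 |
|---|---|---|
| 0 | $199 | -$41 |
| 1 | $249 | +$9 |
| 2 | $299 | +$59 |
| 3 | $349 | +$109 |

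Each month missed in SC moves the difference $40 towards SC+BFI. The documents therefore fix neither the direction nor the size of the realised gap.

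**What does SC pay reward?** Section 10.3 ties the $40 to completed nutritional monitoring. Sections 10.2, 10.5 and 14.1 tie it to completed home visits. A missed appointment counts against the mother on either basis, since 10.3 treats it as non-compliance with monitoring. The two diverge for a visit that takes place without completed monitoring.

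**Is nutritional monitoring confined to SC?** Section 10.3 describes it under SC, but also says that the rest of the SC+BFI procedure matches SC. The monthly-visit list in 10.7 includes a log of the mother's eating without limiting it to an arm. Section 11.1 gives mothers who refuse observation pay for nutritional monitoring. The documents do not settle the question.

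**The case against.** The best defence has four parts.

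1. *The declared element is broad.* Section 10.3 defines it as escalating, contingent on observed BF and paid at once. A reader might infer that faster payment is an undeclared rival explanation. It is not: the lump sum in SC is the stated contrast. This part stands in full, but neither the bonus nor the form of payment falls inside that definition.
2. *The comparability statement can be read as covering the monthly payments only.* On that reading, $270 vs $240 is fair. This also stands, but it leaves the bonus uncontrolled.
3. *The maxima are not payments.* A reader might infer from $420 vs $240 that SC+BFI mothers will receive 75% more. The documents do not support that. Reaching $420 requires BF shown at all six visits and three package selections, and the pilot mean of $199 lies below the SC ceiling. Under a contingent scheme, pay received depends on the outcome, so equal ceilings would not equalise it either.
4. *The comparison itself is sound.* Aim 1 already asks about SC+BFI against SC, and the SAP compares the two groups. No test, endpoint or sample size is affected. This stands, and it limits the point to attribution and wording.

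A reader might also infer that SC alone receives nutritional monitoring, and so a co-intervention of its own. The text is too unclear for that, so it is not counted here as a difference between arms.

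**Conclusion.** The isolation claim is wrong as written. The WIC-package bonus alone contradicts the statement that one element differs, and it accounts for $150 of the $180 gap in maximum pay. The form of payment is a second, lesser difference. This rests on the protocol's own text and needs no assumption. The realised difference of -$41 to +$109 does rest on assumptions: the pilot mean, 0 to 3 bonuses and full SC completion. It shows only that control of the amount is not demonstrated, not that SC+BFI mothers will receive more.

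The randomised comparison remains valid for the whole SC+BFI payment package versus SC. What it cannot support is attributing the effect to the monthly contingent incentive alone. The primary hypothesis should be corrected, but the trial's test is not undermined.

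**What to change.** - In 4.2, 9.5 and 10.3, restate the hypothesis and planned conclusion as the effect of the SC+BFI payment package, including the WIC-package bonus, against SC.
- Remove the word *isolated*, the statement that only one element differs, and the statement that SC pay controls for the amount. Alternatively, reconcile 10.2, 10.3, 10.5 and 14.1 so that all three are true.
- State once what the SC payment rewards, monitoring or visits, and whether nutritional monitoring applies in both arms.
- Add a SAP table of dollars earned per mother by arm and source (monthly incentive, bonus, SC payment, assessments). Keep it descriptive: pay is received after randomisation and depends on BF, so it should not be adjusted for in the primary model.

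No payment amount is proposed. The cost is wording in the protocol and SAP and one table, which the cost tracking under Aim 5 should largely supply. Arms, sample size and payments need not change. The downside is a narrower causal claim.

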Aim 3: To explore the effect of changes in theoretically important variables that may either moderate or mediate the effect of *SC+BFI* on BF and infant outcomes. We include hypothesized non-program factors (see Figure 1) that may moderate treatment efforts.

Aim 4: To explore community- and policy-level factors that may impact the sustainability of an incentive-based intervention with corporate representatives and insurance companies.

Aim 5: To track the intervention and medical costs for cost-effectiveness analyses.

- 4.2 The primary outcome is the BF continuation rate at 6-month postpartum. We hypothesize that the isolated effect of monthly incentives contingent on BF in *SC+BFI* will increase BF rates by 25% at 6-month compared to *SC*. The exploratory outcome is the BF continuation rate at 12-month postpartum. We will hypothesize that *SC+BFI* will increase the BF rate at 12-month, compared to *SC*.

We hypothesize that compared to the *SC* condition, the *SC+BFI* condition will have significantly lower infant weight gain and incidents of ER visits for infants at 3-month postpartum. We hypothesize that participants in *SC+BFI* would evidence greater increases in the motivation and self-efficacy, which, in turn, will account for between-group differences in outcomes.

5.0 Background/Literature Review/Rationale for the Study:

- 5.1 **Background:** Disparities in the health outcomes for mothers and their children exist due to low BF rates. WIC-eligible mothers are identified as at risk for early cessation of BF. Early cessation of BF leads to multiple health risks including increase in mortality and infectious diseases among infants and postpartum health issues. Several promising approaches exist to increase BF duration, including home-based professional and peer lactation support and financial incentives contingent on BF. However, these approaches have never established their efficacy to increase BF duration among low-income mothers.

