2. Participants may feel hesitance or concern completing research measures including breastfeeding observation.

Protections: Participants will be informed of potential hesitance or concern from completing research measures before signing the consent form and will be allowed to refuse to answer any question, provide biological samples, or let research staff observe BF or pumping without penalty. All research staff will be females. In the event of refusing to let research staff observe BF or pumping, mothers will not be eligible for receiving monthly financial incentives contingent on observed BF; however, they receive compensations for monthly nutritional monitoring and periodic assessments as those in the control condition. Their data will not be used for analyses. Direct observation of BF in a home setting has been acceptable to pilot study participants, and no participants refused to demonstrate BF in front of research staff that they built rapport with. Research staff will be trained in how to address hesitance or concern among participants and how to ask observing BF or pumping in a non-invasive manner.

3. Harm resulting from a breach of confidentiality: Breach of confidentiality could include unauthorized persons accessing information contained in their study files.

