Missing values. We will use an intent-to-treat analysis treating missing values for breastfeeding (BF) status as non-BF status. In addition, the mixed effect models will provide valid estimates of efficacy if the proportion of missing values is less than 10%.¹

Interim analyses. Three interim analyses will be conducted to formally monitor the accumulating data in the study, at 2 months, 4 months, and 6 months, with expected increase of BF rate by 25% as a significant increase at 6-month postpartum. With the overall proposed recruitment number of 168 participants, the α -levels are 0.012, 0.016, and 0.022 for 2-month, 4-month, and 6-month postpartum, based on the standardized Z-values for the two groups from the O'Brien-Fleming function with cumulative $\alpha=0.05$ with power of 85%. If we do not see significant increases (at pre-required α -level) either at 2 or 4 months, we will increase the number of participants to recruit to sustain the power.

Logistic regression will be used to compare groups on the primary binary outcomes of point-prevalence of BF status at 1-, 3-, 6-, and 12-month postpartum; survival analyses will also be used to assess continuation. The models will include terms for study group, time, and the group by time interaction. Although propensity score-matched randomization will minimize the need for covariate adjustment, theoretically important covariates and differences will be considered for inclusion in adjusted analyses to improve their precision. Since the 12-month postpartum BF rate is an exploratory outcome, we will use a conservative significance level of .001 versus .05 for BF rates at other time points to decrease the possibility of having a false-positive statistical outcome. The Cochran-Armitage Trend Test will also be used to examine the trend of BF from 1-month through 6-month postpartum and from 1-month through 12-month postpartum. These analyses will also be used to examine the impact of *SC+BF1* on exclusive BF rates at each time point.

References

1. Bennett DA. How can I deal with missing data in my study? *Australian and New Zealand journal of public health*. 2001;25(5):464-469.

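### Mothers who refuse breastfeeding observation are excluded under section 11.1 but counted as not breastfeeding under the SAP, so the 6-month primary rate has two possible denominators

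*Combined protocol and SAP*

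**What the plan says.** Protocol section 11.1, risk 2 (Protections), tells mothers that they "will be allowed to refuse to answer any question, provide biological samples, or let research staff observe BF or pumping without penalty". Of those who refuse observation it says that "mothers will not be eligible for receiving monthly financial incentives contingent on observed BF", and it then adds: "Their data will not be used for analyses". It also reports that in the pilot "no participants refused to demonstrate BF in front of research staff that they built rapport with".

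The SAP (Statistical Design and Power, Missing values) states: "We will use an intent-to-treat analysis treating missing values for breastfeeding (BF) status as non-BF status". It makes no exception for refusal.

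Section 9.5 names the BF continuation rate at 6 months as the primary outcome and fixes how it is measured: "This is determined by observed breastfeeding which includes: audible swallowing", with further signs listed and an equivalent for mothers who pump.

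Observation is requested in both arms. Section 10.3 says for Standard Care (SC): "At each monthly home visit, blinded RA will ask participants to demonstrate BF". The description of the incentive arm (SC+BFI) contains the same request.

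Section 4.2 sets the infant hypotheses: "significantly lower infant weight gain and incidents of ER visits for infants at 3-month postpartum".

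**The concern.** Refusal happens after randomisation. A mother who refuses at month 6 has no observed status, so she meets the SAP's definition of missing and is counted as non-BF. Under section 11.1 she leaves the analysis. The same data then give two primary results. With both rules on paper, the choice between them could be made after the results are seen.

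Section 11.1 is also incomplete as a rule. It does not say which arm it covers, whether a refusal at any visit triggers it, or whether the data of one visit or the mother's whole record is dropped. If the whole record goes, infant weight and emergency room visits are lost as well, although neither needs an observed feed.

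**Working it through.** **Step 1. The rules side by side, for a refusal at month 6.** Let x be the number of mothers observed breastfeeding in an arm of 84 (168 randomised, half to each arm; section 3.1), and r the number who refuse at month 6.

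- SAP rule: rate = x / 84.
- Section 11.1 rule: rate = x / (84 − r).

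A month-6 refuser is never part of x. Exclusion therefore leaves the numerator alone, shrinks the denominator and raises the rate of the arm in which the refusals occur. It favours SC+BFI if they are in SC+BFI, and SC if they are in SC.

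**Step 2. An earlier refusal, with the whole record dropped.** Here the direction is not fixed. Take 34 observed BF of 84 (40.5%) and 4 mothers who refused at an earlier visit.

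- If all 4 were seen breastfeeding at month 6, exclusion gives 30/80 = 37.5%, which is lower.
- If all 4 were observed at month 6 and were not breastfeeding, it gives 34/80 = 42.5%, which is higher.

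**Step 3. Illustration of a changed verdict.** The counts are assumed and chosen near the thresholds. A single two-sided pooled z-test stands in for the planned logistic models and three looks:

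z = (p1 − p2) / √[p̄(1 − p̄)(1/n1 + 1/n2)]

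The reference levels are the SAP's 0.022 for the 6-month look and its general .05.

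| Rule | SC+BFI | SC | Difference (points) | z | p |
|---|---|---|---|---|---|
| SAP rule | 34/84 | 21/84 | 15.5 | 2.14 | 0.033 |
| Drop 4 in SC+BFI | 34/80 | 21/84 | 17.5 | 2.37 | 0.018 |
| Drop 4 in SC | 34/84 | 21/80 | 14.2 | 1.93 | 0.054 |
| Drop 4 in each arm | 34/80 | 21/80 | 16.3 | 2.16 | 0.030 |

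The second row crosses 0.022 in favour of SC+BFI. The third crosses .05 in the other direction. The fourth changes no verdict.

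**Step 4. How often the rules disagree.** Assumptions: month-6 refusals in SC+BFI only; true rates of 45% versus 20%; exact enumeration with 84 per arm. The 20% is the Delaware Medicaid figure in section 5.1, and the planned 25% increase is read as 25 points. The refusal rates are assumed.

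The two rules give different verdicts at 0.022 in this share of trials, where the lower end has all refusers non-BF and the upper end has all of them breastfeeding:

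- 2% refusal: 1.7% to 2.1%
- 8% refusal: 5.9% to 13.6%

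**Step 5. False efficacy.** Assumptions: no true effect, 20% in both arms, and 8% of SC+BFI refusing, all of them non-BF. Exclusion moves the expected SC+BFI rate to 0.20/0.92 = 21.7%. The chance of a significant result in favour of SC+BFI at two-sided .05 is 4.6% under exclusion and 2.6% under the SAP rule.

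**Step 6. The opposite case.** Assumptions: true rates of 45% versus 20%, with 8% of SC+BFI refusing while still breastfeeding. The expected difference is:

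- SAP rule: 0.45 − 0.08 − 0.20 = 17.0 points
- Exclusion: (0.45 − 0.08)/0.92 − 0.20 = 20.2 points

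Both understate the true 25 points, the SAP rule by more. Neither rule is better in every case.

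**The case against.** **Practical effect may be nil.** The documents' only evidence is that no pilot mother refused, and with no refusals the rules coincide. The 2% to 8% range has no source in the documents. This stands as a limit on size. But the pilot statement is qualified by rapport with staff, it rests on 36 mothers, and the protocol itself provides for refusal.

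**The SAP could be read as governing.** It is the dedicated analysis text, and the section 11.1 sentence sits among participant protections. That reading is reasonable, but no precedence is stated, and a specific sentence about refusers can equally be read as an exception to a general missing-data rule.

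**A reader might infer that the exclusion biases the trial towards the incentive.** The sentence on losing the incentive fits SC+BFI most naturally, so one-arm exclusion is a tempting reading. The documents do not support it as a finding. Both arms are asked to demonstrate BF, and the exclusion sentence names no arm. Mothers in SC+BFI are paid for observed BF and so have a reason to accept observation, while SC pay does not depend on it. Refusal by breastfeeding mothers is at least as plausible in SC, where exclusion would weaken the result.

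**Large error rates can be produced but should not be over-read.** With no true effect, a 20% base rate and 8% of SC+BFI refusing while breastfeeding, the two-sided error is 21.9% under exclusion and 29.2% under the SAP rule. That requires 0.08/0.20 = 40% of breastfeeding SC+BFI mothers to refuse. Almost all of the error favours SC, and false efficacy is under 0.1% under both rules.

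**Conclusion.** The contradiction is real and unreconciled. A mother who refuses observation at month 6 is excluded by section 11.1 and counted as non-BF by the SAP, and the exclusion breaks the plan's own intention-to-treat analysis. For month-6 refusals, exclusion raises the rate of whichever arm they are in. If an earlier refusal removes the whole record, the direction is not fixed. It would therefore go too far to say that exclusion always raises the SC+BFI rate.

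The size is hypothetical. Under the assumptions shown, a handful of refusals in one arm can move a borderline result across 0.022 or .05 in either direction. With refusals in SC+BFI only, the rules disagree at 0.022 in about 2% of trials at 2% refusal and 6% to 14% at 8%. The point should be fixed before outcomes are analysed because the repair is small and the conflict bears on the primary outcome. It does not by itself invalidate the design.

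**What to change.** - Delete the section 11.1 sentence, or limit it to say that a refused observation gives no observed BF status at that visit.
- State in the SAP that every randomised mother is analysed in her assigned arm, that a refused 6-month observation follows the existing missing-as-non-BF rule, and that refusers' infant outcomes stay in the secondary analyses. The pilot likewise kept all enrolled mothers in its intention-to-treat analysis (section 5.3).
- Record refusal separately from having stopped BF, and report it by arm and visit.
- Add one labelled sensitivity analysis that classifies refusers in both arms by the daily infant-feeding log already collected at the monthly visits (section 10.7). An analysis excluding refusers is optional.

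The cost is one protocol sentence, a short SAP addition, one table and one analysis, with no added participants or visits. The downside is that counting refusers as non-BF misclassifies those still breastfeeding, as in Step 6. The sensitivity analysis addresses this only in part, because the log is self-reported and a mother may decline it too.
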